17. “Immediate Influence of TES on Pain...” by Gabis et al	17. Feb2003
18. “Change in the Beta Endorphin Levels...” by Airapetov et al	18.
19. Contract including budget	19. 18Oct2017
20. UA PI CV	20. 09Jan2017
21. Responsible Physician CV/biosketch	21.
22. Responsible Physician license	22.
23. Nexalin/Carrier financial information	23. 26Jan2018

See HSPG website for submission requirements.

Items needed for approval:

- Word Versions of Application, Consents, Recruitment and Data Collection
- **F107: Verification of Training Form**
- **Current PI/Co-PI CVs or biosketch**, if not included with copy of grant application
- **Informed Consent/Permission/Assent Form(s)** – including study specific release of information documents, DHHS approved sample consent forms. If consent will not be documented in writing, a script of information to be provided orally to subjects

Other Items as applicable:

- **Appendix A - Children**
- **Appendix B - Drug/Device**
- **Appendix C- Multi Site Research**
- **Appendix D- Pregnant Women and Neonates**
- **Appendix E- Prisoners**
- **Appendix F- Waiver of Consent/ PHI**
- **Appendix G- Exception from Informed Consent (EFIC)**
- **Appendix H- Native American**
- **Biosafety Review letter** (for UA - Institutional Biosafety Committee)
- **Certificate of Confidentiality**
- **Compressed Gases Review letter** (for UA – Research Instrumentation)
- **Contract** – complete or draft copy of contract including budget
- **Data Collection Tools** – surveys, questionnaires, diaries not included in the protocol, data abstraction form for records review
- **Data Monitoring Charter and Plan**
- **Drug/Device information** – Investigator's Brochure, drug product sheet, device manual, user's manual, instructions for use, package insert, IND/IDE documentation, FDA 1572 form, 510k indication, FDA exemption, sponsor determination of device risk, etc.
- **Export Control Review**
- **Grant Application(s)** – cover-to-cover copy of grant, regardless of home institution or funding agency, and a copy of the Notice of Grant Award.
- **Multi-site information** (for sites engaged in research where the UA is the IRB of record)
 - Copy of any approvals granted from that site (including determinations if this site has an IRB of its own)
 - Site-specific F107
 - Copy of the site's human subjects training policy
 - CV and medical license (if applicable) of site PI
- **Other Approval letters** (e.g., school districts, Tribal, other IRB approvals)
- **Participant Materials** – written materials to be provided to or meant to be seen or heard by subjects (e.g. study newsletter, physician to participant letter, wallet cards, incentive items, holiday/birthday cards, certificates, instructional videos/written guides, calendars, certification of achievement, etc.)
- **Payer coverage analysis**
- **PHI Authorization Form(s)**
- **Protocol** – including all amendments/revisions, sub- or extension-studies
- **Radiation Safety Review letter**- needed regardless if the radiation device is approved and used standard of care
- **Recruitment Materials** – telephone scripts, flyers, brochures, websites, email texts, radio/television spots, newspaper advertisements, press releases, etc.
- **Scientific Review Committee** letter (for cancer related projects – AZCC SRC; other units as applicable if the unit has a scientific review committee)
- **Site Authorizations** for research purposes and/or access to administrative records/samples
 - External sites (such as schools, other hospitals or campuses, etc.)
 - UAHS Research Portal feasibility review approval
- **Travel Authorization documentation** (for UA – Office of Global Initiatives)
- **Use of retrospective research samples and/or data** – IRB approval letter, original consent under which samples/data were collected, letter allowing access to samples

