12. Nicotine use questions: Addresses how much, if any nicotine products (cigarettes, cigars, vapes, chewing tobacco, Nicorette gum, nicotine patches, etc.) were used in a 24 hour timespan
- 13.
14. Physical Measures: Height, Weight, Blood Pressure: To evaluate basic health measures, all subjects will undergo a basic assessment of height, weight, and blood pressure, using standard clinic equipment.
15. Expectancy: Subjects will be asked to rate on a 100mm visual analog scale, the degree to which they agree with the following statements: (1) This treatment will work, (2) This treatment will help my depression, (3) This treatment will help my anxiety, (4) This treatment will help my sleep, (5) This treatment will improve my quality of life.

Following this baseline assessment, patients will be randomized to receive either Nexalin or Sham treatment. Randomization will occur, such that for every 20 subjects enrolled, 10 will receive Nexalin

and 10 will receive Sham treatment. Sponsor will provide two different devices, identical in appearance and pre-labelled with a sticker (fairy or puppy). One will produce an electrical current, whereas the other will not. Each participant will be assigned a randomization code (fairy or puppy) according to the order of a randomization list generated. Random number generation will be accomplished using the Excel RAND() function.

Nexalin treatment involves placing three conductive pads on the head (one on the forehead and one behind each ear). The patient then sits as the device administers the current through the pads. The default current level for the Nexalin ADI Device is 15.00 mA. This is not adjustable. The treatment is painless. In most cases, patients cannot feel when the pads are activated at all. The pads are activated for 40 minutes during each administration. The Sham treatment will be identical using the same setup procedure, with the exception that there will be no current through the electrodes. Since the Nexalin treatment is undetectable, this will exactly mimic active treatment. Neither subjects nor the study staff will be informed whether they receive active Nexalin or sham treatment, though this information will be made available if medically necessary.

Please see the Nexalin device manual for specific device setup instructions.

All visits will occur on an inpatient basis.

1. Patients will be taken to a standard clinic room, where they would normally meet with their mental health care provider.

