2. The health care provider will ask the about their experiences during the week and address any problems with the study.
3. A licensed provider trained on using Nexalin will administer the treatment in two 40 minute sessions. Sessions will occur AM and PM.
4. Subjects will then be free to leave until their next appointment.

During each subsequent treatment visit, subjects will complete the following questionnaires:

1. SAFTEE Physical symptom inventory (see above)
2. Profile of Mood States: The POMS is a standard self-report instrument that assesses clinical and sub-clinical mood symptoms
3. Modified Brief Substance Craving Scale
4. Nicotine use questions: Addresses how much, if any nicotine products (cigarettes, cigars, vapes, chewing tobacco, Nicorette gum, nicotine patches, etc.) were used in a 24-hour timespan
5. Faces rating scale: The scale shows a series of faces ranging from a happy face at A which represents "Happy" to a sad face at G which represents "Feeling bad/sad." Participants will rate their feelings before and after each TES treatment

Also, every three treatments, in addition to the treatment visit questionnaires subjects will also complete the following questionnaires that were administered at baseline: PHQ-9, GAD-7, and ISI.

The final assessment (*after treatment 15*) will include re-administration of all baseline measures, completed at the final treatment visit, with the exception that Expectancy measures will reflect on the treatment, subjects will be asked to rate on a 100mm visual analog scale, the degree to which they agree with the following statements: (1) This treatment worked, (2) This treatment helped my depression, (3) This treatment helped my anxiety, (4) This treatment helped my sleep, and (5) This treatment improved my quality of life.

Thus, each patient will be in STUDY 1 for 10 to 16 treatments in a 5 to 8 day period, 2 sessions per day. Sessions will be conducted in AM and PM. Subjects will be allowed to miss up to 5 treatment sessions within the 1-month treatment window. Any additional missed appointments that are not made up in the stated time frame will be withdrawn from the study.

ANALYSIS PLAN

The results of administering the various tests in a number of metrics that are taken are 4 points:

Pre Treatment

After 5 Treatments

After 10 Treatments

After 15 Treatments

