We will compare sham vs Nexalin by measurement over the 4 periods. Comparisons will be done on an absolute basis, percentage basis, from start to measuring point, and for each interval.

9) Cost to subjects

There are no costs to subjects save for their time.

10) Risks to subjects

Risks associated with scheduling and potentially delaying treatment:

Since subjects will still be receiving usual care during the study period, no subjects will be deprived of care at any time.

Risks associated with Nexalin treatment:

Transcranial electric stimulation devices are classified as a Class III device. These types of devices have been used for many years and occasional adverse effects have been reported, including headache, dizziness, nausea, minor burns, increased agitation, minor skin irritation from specific electrodes, and electrical discharge when electrodes are removed. Specifically, headaches and nausea have been noted when current levels are higher than those used in the present study.

To avoid headaches and nausea, lower currents will be used. Patients shall also be instructed to alert the technician if they experience headache or nausea. If the condition continues, treatment will be discontinued. Burn occurrence can be avoided by using lower current (as is in the case for this study), large area electrodes, and by the device's ability to monitor electrode impedance and stop treatment if electrode contact is poor. The device generates no DC current and thus no significant electrolysis will occur in the electrodes. The AC waveform is passed through a charge blocking capacitor to patient electrodes for further patient protection. Rarely, patients have been noted to experience excitability or heightened nervousness during treatment. The technician administering treatment shall be trained to identify such cases and instructed to discontinue treatment as appropriate. If agitation persists for a patient, the licensed health care practitioner may discontinue treatment. Rashes from specific electrodes may occur in patients sensitive to the chemistry used. The possibility of such rashes or skin irritation has been minimized by maintaining charge balance in the output waveform so significant electrolysis does not occur at the electrode/skin interface, and by using glycerol coated electrodes that result in little or no skin irritation. Additionally, collection of patient sensitivity information prior to

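### The final battery and last analysis point sit after treatment 15, but compliant courses may end at 10 to 14, so that comparison covers only a subset selected after randomisation

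*Protocol*

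**What the plan says.** All of this is in the Protocol, Section 3, item 8 (research procedures and Analysis Plan), unless noted.

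- **Final assessment.** "The final assessment (*after treatment 15*) will include re-administration of all baseline measures". The sentence goes on to place this at the last treatment visit.
- **Analysis points.** There are four: before treatment, and after 5, 10 and 15 treatments, the last given as "After 15 Treatments". The planned contrast is "We will compare sham vs Nexalin by measurement over the 4 periods".
- **Course length.** "each patient will be in STUDY 1 for 10 to 16 treatments in a 5 to 8 day period, 2 sessions per day". Inclusion criterion 3 (item 6) asks for availability for 10 to 15 treatments over the same number of days.
- **Missed sessions.** "Subjects will be allowed to miss up to 5 treatment sessions within the 1-month treatment window". Beyond that, "Any additional missed appointments that are not made up in the stated time frame will be withdrawn from the study".
- **Interim scales.** "Also, every three treatments, in addition to the treatment visit questionnaires subjects will also complete the following questionnaires"; these are PHQ-9, GAD-7 and ISI. SAFTEE, POMS and the craving scale are completed at every treatment visit after baseline.
- **Setting.** "All visits will occur on an inpatient basis".
- **Other exits.** Item 10 provides for stopping treatment for continuing headache or nausea and for persistent agitation, and for discontinuing suicidal subjects. Item 17 lets study staff withdraw subjects. No later assessment is described for any of them.

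**The concern.** The last assessment is defined by the number of treatments received, and the protocol allows that number to vary. A subject can follow every rule, stop at 10 to 14 treatments, and have no value at the last analysis point. Whether a subject reaches treatment 15 is settled after randomisation by length of stay, attendance, tolerability and clinical state.

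This bears on the main question. The primary outcomes are depressive, anxiety and insomnia symptoms, and PHQ-9, GAD-7 and ISI are the scales that match them. If reaching treatment 15 is related to outcome and differs by arm, the after-15 contrast is no longer a comparison of the randomised groups. Even without bias, it is made on fewer subjects than were randomised. Earlier values of the three scales could represent subjects who stop early, but as the schedule stands those values belong to no analysis point.

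**Working it through.** **Inputs from the protocol:** 2 sessions a day; 5 to 8 days; 10 to 16 treatments; up to 5 missed sessions; final battery and last analysis point after treatment 15; PHQ-9, GAD-7 and ISI every 3 treatments; post-baseline analysis points 5, 10 and 15; 150 subjects allocated 1:1.

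**1. The stated course length.** Sessions = 2 × days. 2 × 5 = 10 and 2 × 8 = 16, which reproduces the protocol's range.

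**2. Which courses reach treatment 15.** Treatment 15 needs 15 / 2 = 7.5 days, that is, an eighth day.

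| Days | Sessions available | Reaches 15? |
|---|---|---|
| 5 | 10 | no |
| 6 | 12 | no |
| 7 | 14 | no |
| 8 | 16 | yes, if at most 1 is missed and not replaced |

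On an 8-day course, 0 to 5 unreplaced misses leave 16, 15, 14, 13, 12 or 11 treatments, so 2 of the 6 permitted miss counts reach 15. Of the 7 permitted course lengths (10 to 16), 5 fall short. Under inclusion criterion 3 (10 to 15), 5 of 6 fall short. These are counts of permitted options, not proportions of subjects.

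**3. Where the three scales meet the analysis points.** Collection, counting from the first treatment, is at {3, 6, 9, 12, 15}. The post-baseline analysis points are {5, 10, 15}. The two sets share only {15}, the point that short courses miss.

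**4. What early stoppers do contribute.** The last multiple of 3 reached is 9 for courses of 10 or 11, and 12 for courses of 12, 13 or 14. The gaps to the last treatment are 1, 2, 0, 1 and 2 sessions. Near-final values are thus scheduled, but none falls on an analysis point.

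**5. Illustration of the consequences, on assumed inputs.** The protocol states no alpha, power, effect size or share reaching treatment 15.

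*Precision.* Assume 75 per arm, two-sided 0.05, 80% power and a share s of each arm reaching treatment 15. The detectable difference in SD units is (1.960 + 0.842) × √(2 / (75s)).

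| s | Subjects | Detectable difference (SD) |
|---|---|---|
| 100% | 150 | 0.46 |
| 80% | 120 | 0.51 |
| 70% | 105 | 0.55 |
| 50% | 75 | 0.65 |

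*Bias.* Assume no true effect, and a correlation of 0.2 to 0.4 between outcome and the tendency to stay. A simulation gives these spurious differences between arms:

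| Share reaching 15 in the two arms | Spurious difference (SD) |
|---|---|
| 70% and 70% | about 0 |
| 80% and 60% | 0.06 to 0.12 |
| 90% and 50% | 0.12 to 0.24 |

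**The case against.** **The final visit may be each subject's own last visit.** On that reading treatment 15 only labels the nominal full course, and the battery already exists for short courses. The wording allows this, although the same sentence attaches the assessment to treatment 15. It does not rescue the analysis: a battery given after 11 to 14 treatments matches none of the four points. The only PHQ-9, GAD-7 and ISI values at 10 would come from subjects who stopped there, which is another selected group.

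**Fifteen may be the target and ten the tolerance.** Fifteen less five permitted misses is exactly ten, and missed sessions may be made up within a one-month window. Some subjects could reach 15 that way. But the window conflicts with the 5 to 8 day period, visits are inpatient only, and a permitted 10-treatment course is not extended by it.

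**Little information is lost, and the SAP can use it.** Values within two sessions of the end are scheduled for compliant early stoppers, the after-15 point is not named as primary, and nothing restricts the analysis to completers. An unseen SAP could model the values at 3, 6, 9 and 12. This stands in part: it would reduce the loss. A SAP cannot supply final batteries or post-withdrawal values that were never collected, and the protocol itself names 5, 10 and 15.

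**Masking limits differential loss.** It makes it less likely. It does not exclude it: headache, nausea and agitation are listed as risks of stimulation, while sham risks are limited to nervousness and skin irritation.

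**The 3-versus-5 mismatch is a separate defect.** It would exist even if everyone completed the course. It matters here because it leaves treatment 15 as the only post-baseline analysis point at which these scales are scheduled. SAFTEE, POMS and craving are not affected in this way, since they are taken at visits 5 and 10.

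**Conclusion.** The concern holds and should be fixed. The protocol fixes its final battery and last comparison at a treatment count that its own rules do not require subjects to reach. Within the stated period, 3 of the 4 permitted durations cannot reach it, and the 8-day course reaches it only with at most one unreplaced miss. For PHQ-9, GAD-7 and ISI it is also the only post-baseline analysis point that coincides with collection. As written, the after-15 contrast on these scales is a completer comparison.

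The number of the 150 affected cannot be derived, because no stay-length or attendance figures are given; if nearly everyone stays eight days and attends, the effect is small. Bias between arms further requires that reaching treatment 15 differ by arm and relate to outcome. The precision and bias figures rest on assumed inputs and show scale only. The conflict between course rules and assessment schedule rests on no such assumption.

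**What to change.** 1. Give the full final battery at each subject's last study visit, whatever the number of treatments received.
2. Continue PHQ-9, GAD-7 and ISI up to discharge in subjects whose study treatment stops or who are withdrawn from treatment, unless they withdraw consent.
3. Compare all randomised subjects at this end-of-course assessment, and report number of treatments and days by arm.
4. Keep the after-15 contrast as a supportive analysis, labelled as completers only.
5. Set the earlier analysis points at treatments where the three scales are actually taken.

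The cost is protocol wording and one extra questionnaire set for early stoppers, who are inpatients. The downside is that the end-of-course contrast averages over different exposures: 10 to 16 treatments, and fewer in those withdrawn. Reporting exposure by arm makes that visible.

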Adverse events will be reported electronically by Carrier Clinic to the UA PI via the Adverse Event Report, located on pages 12-13 of the Data Collection Instruments (*NEXALIN data collectN instruments.pdf*), which will be used to collect required AE information. Clinicians will submit all forms as they take the information and data is available to the UA PI in real time. The form contains a provision for ongoing events and further information if required. If adverse events to Nexalin

treatment occur clinicians will use their discretion to handle the situation and report immediately through the tracking form.

The UA PI will review all AE's, serious and otherwise, for submission to the UA IRB per its submission requirements. Unblinding of the treatment received– active Nexalin or sham– will occur if medically necessary to protect the safety of subjects.

16) Medical care and compensation for injury

If subjects experience an adverse event or injury as a direct result of participation in the study, they are instructed to seek treatment and inform their study doctor. The study doctor can assist them in obtaining appropriate medical treatment. If a subject has Medicare or other government health insurance, Nexalin Technologies, Inc. will pay for reasonable medical expenses associated with the treatment of injuries directly resulting from taking part in this research. If a subject has private insurance, Nexalin Technologies, Inc. will pay for these costs to the extent they are not covered by the subject's private insurance. Subjects' health care payers/insurers may not cover costs of research-related injuries.

The University of Arizona and Carrier Clinic have no funds set aside for the payment of treatment expenses resulting from participation in this study. In addition, there are no plans for the University of Arizona or Carrier Clinic to provide other compensation for study-related injuries.

17) Withdrawal of subjects

If disqualifying information/conditions are discovered during screening or at any point during the study, or if it becomes evident that the participant is unable or unwilling to comply with study procedures, research study staff may withdraw that individual from the study.

Subjects can voluntarily withdraw from the study at any time by speaking with the PI or study team. The study staff will then ensure the subject withdraws from the study safely and will provide any necessary follow-up care.

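### Randomised participants who exceed the missed-session limit leave the study, not only treatment, and no outcome assessment is provided for them afterwards

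*Protocol*

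**What the plan says.** Patients are randomised 1:1 after the baseline assessment (Protocol, Section 3, item 8). The same item sets the allowance, "Subjects will be allowed to miss up to 5 treatment sessions within the 1-month treatment window", and the consequence of exceeding it, "Any additional missed appointments that are not made up in the stated time frame will be withdrawn from the study". The grammatical subject of that sentence is the appointments, but only participants can be withdrawn. Item 17 (Withdrawal of subjects) adds a discretionary rule for anyone found "unable or unwilling to comply with study procedures, research study staff may withdraw that individual from the study".

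Collection of the primary outcomes is tied to treatment. For the ISI as for the other two scales, item 8 sets this schedule: "every three treatments, in addition to the treatment visit questionnaires subjects will also complete the following questionnaires that were administered at baseline: PHQ-9, GAD-7". At the end of the course, the last assessment is labelled as following treatment 15 and consists of "re-administration of all baseline measures, completed at the final treatment visit". Item 17 mentions safe withdrawal and necessary follow-up care after voluntary withdrawal, which is clinical care. The protocol describes no early-termination visit and no outcome assessment off treatment.

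The course to which the limit applies is given in item 8 as "10 to 16 treatments in a 5 to 8 day period, 2 sessions per day", but in item 6 (inclusion criterion 3) as 10 to 15 treatments over 5 to 8 days. The allowance itself refers to a 1-month window.

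**The concern.** The three primary outcomes are reductions in depressive, anxiety and insomnia symptoms, which PHQ-9, GAD-7 and ISI measure. A rule that ends study participation because of poor attendance also ends collection of those scores, for a group selected by something that happened after randomisation. If attendance is related to how the participant is doing, the scores that remain no longer represent the randomised arms, and the Nexalin versus sham comparison can be biased in either direction.

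An analysis plan can choose how to handle missing scores, but it cannot collect them. Whether assessment continues after treatment stops is decided by the protocol.

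**Working it through.** **1. What the text provides.** Side by side, the four relevant provisions are:
- Withdrawal for excess missed sessions is from the study (item 8).
- Withdrawal for non-compliance is from the study (item 17).
- PHQ-9, GAD-7 and ISI fall due after every third treatment (item 8).
- The final assessment falls at the final treatment visit (item 8).

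A participant who has been withdrawn receives no further treatments, so nothing triggers a further score.

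**2. Counts.** More than 5 sessions missed and not made up means at least 6 missed.
- 15-session course: at most 15 − 6 = 9 treatments received, so at most 9/3 = 3 of 15/3 = 5 three-treatment assessments.
- 16-session course: at most 16 − 6 = 10 treatments, so at most 3 of 5 (whole parts of 10/3 and 16/3).

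Someone who misses the allowed 5 of 15 also receives 10 treatments and has at most 3 of these assessments. The count alone therefore does not measure the cost of the rule. The cost is that withdrawal closes off everything later, including the final assessment.

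**3. Size of bias: illustration only.** The protocol gives no withdrawal rate, SD or effect size, so there is no stated figure to reproduce. From the protocol: 150 participants at 1:1, so 75 per arm. In SD units the standard error is √(2/75) = 0.163.

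Assumptions: final score is N(0,1) on sham and N(−0.4,1) on Nexalin, higher is worse. A withdrawal variable W has unit variance and correlation ρ with the final score. Participants with W above a common threshold c are withdrawn, and c is set so that a proportion p of sham is withdrawn.

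Retained mean, sham: −ρφ(c)/(1 − p). Retained mean, Nexalin: −0.4 − ρφ(c + 0.4ρ)/(1 − p_N), where p_N = 1 − Φ(c + 0.4ρ).

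Worked for ρ = 0.5, p = 10%: c = 1.282, so the sham mean is −0.0975. On Nexalin the threshold is 1.482, p_N = 6.9% and the mean is −0.4715. The difference is 0.374, a bias of 0.026.

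| Sham withdrawn | ρ = 0 | ρ = 0.5 | ρ = 1 (extreme) |
|---|---|---|---|
| 5% | 0.400 | 0.383 | 0.342 |
| 10% | 0.400 | 0.374 | 0.307 |
| 15% | 0.400 | 0.367 | 0.279 |

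At ρ = 0.5 the bias is 0.017 to 0.033 SD.

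*Using an earlier score* (assumed Nexalin mean −0.3, correlation 0.6 with the final score; regression within arm; simulation): if withdrawal follows the final score the estimates are 0.391 / 0.382 / 0.377, a bias of about 0.01 to 0.02. If it follows only the earlier score there is no bias.

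*No true effect*, 5% versus 3% withdrawn, ρ = 0.5. Let λ(p) = φ(z)/(1 − p), with z the upper-p normal quantile; λ = 0.109 and 0.070.
- Both arms lose poor scorers: 0.5 × (0.109 − 0.070) = 0.019 SD, type I error about 5%.
- Loss related to outcome only in the 5% arm: 0.5 × 0.109 = 0.054 SD, about 6%.
- Arms lose opposite ends: 0.5 × (0.109 + 0.070) = 0.089 SD, about 8%.

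**4. How much could be avoided.** With p = 10% and ρ = 0.5, if 0, 25, 50, 75 or 100% of those withdrawn are still assessed, the bias is 0.026, 0.019, 0.012, 0.006 or 0 SD. These shares are assumed.

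**The case against.** The best counter-argument is that the avoidable harm is small. In the common-threshold case at ρ = 0.5 the bias is a fraction of the standard error, and an earlier score reduces it. The 8% type I error needs the arms to lose opposite ends, for which the protocol gives no basis, since it describes stimulation that cannot be felt and an identical sham. Missed sessions can also be made up, and someone still short by then may have left the unit and be out of reach. All of this stands, and it limits the weight of the point. It does not remove it: the loss is written into the rule, and assessing those who are still present costs little.

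Three stronger readings are tempting but not supported.

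- *Withdrawal costs the participant the after-10 and after-15 values listed in the analysis plan.* Primary scores taken every three treatments fall at 3, 6, 9, 12 and 15, so on that schedule nobody has one at 5 or 10. A participant who misses the allowed 5 of 15 sessions also never reaches treatment 15. Neither gap is specific to withdrawal.
- *Withdrawn participants are excluded from the analysis.* The protocol does not say so. Their earlier scores exist and can be used.
- *Stopping for side effects produces the same loss.* Item 10 says "If the condition continues, treatment will be discontinued" and "If agitation persists for a patient, the licensed health care practitioner may discontinue treatment", but treatment there may mean only the session in progress.

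Nor should the limit be subtracted from a 10-session course: 10 equals 15 − 5, so the lower end of the range may already contain the allowance.

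**Conclusion.** The point holds on the text. Randomised participants who exceed the missed-session limit are withdrawn from the study, those judged non-compliant may be, and the protocol provides no later measurement of the primary outcomes for either group. The size of the resulting bias cannot be derived from the document. It is near zero if withdrawal is unrelated to outcome, in which case only precision is lost. It is about 0.02 to 0.03 SD in the moderate common-threshold illustration, and larger if the loss differs in kind between arms or follows the outcome much more closely. Every rate and correlation behind these figures is assumed. This is a change that should be made because it is cheap and cannot be made good at analysis; it is not a flaw that invalidates the trial.

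**What to change.** In Section 3, items 8 and 17, separate stopping study treatment from leaving the study. Participants who exceed the missed-session limit or are stopped for non-compliance, and who remain on the unit, complete PHQ-9, GAD-7, ISI and the final assessment at the times these would have fallen due had sessions continued. They are compared in the arm to which they were randomised. The exceptions are withdrawal of consent and a clinician's judgement that assessment is inappropriate. Clinical stopping rules stay as they are.

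Reconcile the statements that decide who exceeds the limit: 10 to 15 sessions (item 6) against 10 to 16 (item 8), and the 5-to-8-day period against the 1-month window.

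The cost is some protocol wording and a few brief questionnaires for participants already on an inpatient unit. The estimate will then include early stoppers. Those who leave the unit are still lost, so only part of the missing data is avoided.
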